8.3. ANTIBODIES

The appropriateness of the approach taken to analyze and report anti-drug antibody data should be evaluated on a case-by-case basis (*Assay Development [Draft Guidance] 2016*), following recent regulatory guidance and a white paper (*Shankar 2014*). Analysis of antibodies against drug (ADA) will include (but not be limited to) the following tabulated summaries of antibody frequencies and percentages:

1. Incidence of pre-existing anti-hGH binding antibodies (positive Baseline)
2. Incidence of treatment induced anti-hGH binding antibodies by positive types (treatment emergent positive and treatment boosted positive) and overall
3. Incidence of persistent anti-hGH binding antibodies by positive types and overall
4. Incidence of transient anti-hGH binding antibodies by positive types and overall
5. Incidence of treatment induced anti-hGH neutralizing antibodies by positive types and overall
6. Incidence of persistent anti-hGH neutralizing antibodies by positive types and overall
7. Incidence of transient anti-hGH neutralizing antibodies by positive types and overall
8. Incidence of pre-existing anti-PEG antibodies (positive Baseline)
9. Incidence of treatment induced anti-PEG binding antibodies by positive types and overall
10. Incidence of persistent anti-PEG antibodies by positive types and overall
11. Incidence of transient anti-PEG antibodies by positive types and overall

Neutralizing antibodies are defined as confirmed binding anti-hGH antibodies that are confirmed positive in a cell-based neutralizing antibody assay.

In addition, treatment induced anti-hGH binding, anti-hGH neutralizing antibodies, and anti-PEG antibodies will also be summarized by visit and positive types and overall.

Treatment induced ADA will include two positive types:

- Treatment emergent positive: if baseline (pre-treatment sample) is negative for ADA and post-treatment sample is positive for ADA
- Treatment boosted positive: if baseline (pre-treatment sample) is positive and post-treatment sample has a titer which is at least 4-fold higher than the pre-treatment sample.

Transient ADA is defined as treatment-induced ADA detected only at one sampling time point during study, or when there is less than 16 weeks between the first and the last ADA positive post-treatment samples.

Persistent ADA is defined as when there is more than (or equal to) 16 weeks between the first and the last ADA positive post-treatment samples.

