5.3. VISIT WINDOW

Enrolled subjects will attend a total of 3 morning trial visits:

- Visit 1 will be considered Week 1, Day 1 (first day/week of dosing)
- Visit 2 will be performed during Week 13 (± 1 week), 5 days (± 1 day) post-dose
 - If during Week 12, Visit 2 must occur on Days 82 to 84
 - If during Week 13, Visit 2 must occur on Days 89 to 91
 - If during Week 14, Visit 2 must occur on Days 96 to 98
- Visit 3 will be performed during Week 26 (± 1 week), 5 days (± 1 day) post-dose
 - If during Week 25, Visit 3 must occur on Days 173 to 175
 - If during Week 26, Visit 3 must occur on Days 180 to 182
 - If during Week 27, Visit 3 must occur on Days 187 to 189

Subjects <3 years old at Visit 1 will have a total of 4 morning trial visits including the above 3 visits and the addition of:

- C_{max} Visit to be performed during Week 4 (+1 week), 1-2 days after the 4th or 5th dose
 - If during Week 4, C_{max} Visit must occur on Days 23-24
 - If during Week 5, C_{max} Visit must occur on Days 30-31

Post-baseline unscheduled visit (occurred after the date of initiation of the first dose) or end of study visit (early termination visit) will be mapped to the post-baseline scheduled visit with the closest target study day for each scheduled assessment according to [Table 2](#). If the unscheduled visit is in the middle of two scheduled visits, map it to the later one. After mapping, if there are more than one visit in the same window, the visit closer to the target assessment day will be used. If more than one visit has the equal distance to the target day then the later one will be used, if more than one visit on the same day, use the time or the sequence number to select the later record. For listings and shift tables, all data points will be included.

Table 2: Analysis Window

Visit	Screening	Visit 1	C _{max} Visit	Visit 2	Visit 3/ET
Week	Weeks -4 to -1	Week 1	Week 4 (+ 1 Week)	Week 13 (± 1 Week)	Week 26 (± 1 Week)
Target Day		Day 1	Day 29	Day 92	Day 183
Range		Day 1	Day 2 - 60	Day 61 - 137	Day 138 - EOS

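### On the permitted visit days the SAP's 16-week rule for persistent antibodies cannot be met, so antibodies found at both post-dose visits are tabulated as transient

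*SAP*

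**What the plan says.** SAP 8.3 lists eleven antibody summaries. For anti-hGH binding, anti-hGH neutralizing and anti-PEG antibodies in turn, it plans the incidence of treatment-induced (items 2, 5, 9), persistent (items 3, 6, 10) and transient (items 4, 7, 11) antibodies. Items 1 and 8 cover antibodies already present at baseline.

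The definitions are:
- **Persistent:** "more than (or equal to) 16 weeks between the first and the last ADA positive post-treatment samples".
- **Transient:** "Transient ADA is defined as treatment-induced ADA detected only at one sampling time point during study", or first and last positives less than 16 weeks apart.
- **Treatment-induced:** either negative at baseline and positive afterwards, or boosted. Boosted means "baseline (pre-treatment sample) is positive and post-treatment sample has a titer which is at least 4-fold higher than the pre-treatment sample".

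The section opens by saying that the appropriateness of the approach "should be evaluated on a case-by-case basis", and its list is open-ended. It adds that treatment-induced antibodies of each kind "will also be summarized by visit and positive types and overall".

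Sampling is set by the footnotes to SAP Table 1 and by protocol 11.10.1 to 11.10.4. Antibodies are tested at Screening (before treatment), Visit 2 and Visit 3/ET. The Cmax Visit panel has no antibody test.

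SAP 5.3 fixes the visit days, as does protocol 10.2.2. For Visit 2 the earliest are "If during Week 12, Visit 2 must occur on Days 82 to 84" and the latest "If during Week 14, Visit 2 must occur on Days 96 to 98", with Days 89 to 91 between. For Visit 3 the earliest are "If during Week 25, Visit 3 must occur on Days 173 to 175", followed by Days 180 to 182 and Days 187 to 189.

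**The concern.** A rule that sorts antibodies by duration needs a sampling schedule on which both outcomes can occur. Here the only two scheduled post-dose samples appear to be closer together than the threshold. If so, a table reporting no persistent neutralizing antibodies would come out the same whether every affected child cleared the antibody or every one was still positive at the last sample. A child whose antibody first appears at the last sample would also be called transient, although nothing is known about its duration.

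Safety is the primary objective and antibody incidence a secondary one. A reader of the study report could take a structural zero as evidence that antibodies did not last.

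**Working it through.** **Inputs.** The threshold is 16 × 7 = 112 days (SAP 8.3). Permitted Visit 2 days are 82–84, 89–91 and 96–98. Permitted Visit 3 days are 173–175, 180–182 and 187–189 (SAP 5.3).

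**Reproducing the plan's days.** The dose of week w falls on Day 7(w − 1) + 1, and the visit is 5 ± 1 days later.
- Week 12: dose on Day 78, visit on Days 82–84.
- Week 27: dose on Day 183, visit on Days 187–189.

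The other four windows reproduce in the same way.

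**Gap between the two scheduled samples.** There are 9 × 9 = 81 permitted day pairs.

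| Case | Gap in days | Short of 112 by |
|---|---|---|
| Shortest: Day 98 to Day 173 | 75 (10.7 weeks) | 37 |
| Table 2 targets: Day 92 to Day 183 | 91 (13 weeks) | 21 |
| Longest: Day 82 to Day 189 | 107 (15.3 weeks) | 5 |

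No pair reaches 112 days, and only 6 of 81 reach even 15 weeks (105 days). Counting both end days in the longest gap gives 108, still too few. If any day of Weeks 12–14 (Days 78–98) and Weeks 25–27 (Days 169–189) is allowed, the longest gap is 189 − 78 = 111 days, one day short. An early termination sample in place of Visit 3 would normally come sooner and shorten the gap.

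**Resulting labels on schedule, for treatment-induced antibodies.**

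| Visit 2 / Visit 3 | SAP label | Reason |
|---|---|---|
| + / + | transient | first and last positives less than 16 weeks apart |
| + / − | transient | one time point |
| − / + | transient | one time point, duration unknown |

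So items 3, 6 and 10 are zero, and items 4, 7 and 11 equal items 2, 5 and 9. Six of the eleven summaries carry no information on duration. Only the + / − row is labelled in line with what was observed.

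**What could reach 112 days.** With Visit 3 on Day 189, the first positive must fall on or before 189 − 112 = Day 77. With Visit 2 on Day 82, the last must fall on or after 82 + 112 = Day 194. Both are outside the permitted days. The Table 2 analysis ranges (Day 61–137, and Day 138 to end of study) would still accept such samples.

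**How many children.** The only antibody frequency in the documents is in protocol 5.3: one anti-hGH positive child among 12 + 14 + 14 = 40 on TransCon hGH in the pediatric phase 2 trial, or 2.5%. The exact (Clopper-Pearson) 95% interval is 0.06% to 13.2%. Applied to 150 children, this gives 3.75, with an interval of 0.1 to 19.7. No anti-PEG frequency is given.

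**The case against.** The strongest defence is that nothing the trial set out to measure is affected. The stated objective and endpoints concern the incidence of antibodies, not their persistence, and the antibody summaries are descriptive in a single-arm trial. By-visit tables are planned, SAP section 8 promises listings of all safety evaluations, and the list in 8.3 is open-ended. A child positive at both visits can therefore be found in the listings, and an extra row could be added without redefining anything. This stands, and it is why the point is minor. It does not remove the point: by-visit counts do not show whether the same child was positive twice, and the case-by-case and open-ended wording supplies no alternative to the fixed definitions.

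A second defence is that the zero depends on adherence. This also stands. A reader might infer that the persistent tables must be empty whatever happens, but the documents do not support that: an out-of-window visit or an unscheduled antibody sample could give 112 days. Persistence would then be detectable only through a schedule deviation or unplanned sampling. Protocol 10.2.3 provides only for focused assessments at unscheduled visits.

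A reader might also infer that the antibody results as a whole, or the protocol 9.6.2 provision on neutralizing antibodies, are compromised. Neither follows. Treatment-induced incidence does not use the 16-week rule, and the 9.6.2 provision refers to neutralizing status, not duration.

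**Conclusion.** The point holds, with limited reach. For subjects sampled on the permitted days, 16-week persistence cannot be observed, and every treatment-induced antibody is labelled transient. The arithmetic needs no assumption beyond adherence to the schedule. The consequence is a misleading descriptive label in the reassuring direction. Severity is minor.

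The number of children mislabelled is unknown. It is tempting to read the figure of about 4 of 150 (0 to 20) as that number, but it counts all anti-hGH positives. Children positive at Visit 2 and negative at Visit 3 are correctly called transient, and the documents give no split, so the figure is a ceiling under the assumed rate. That rate rests on one child, the predecessor product and treatment-naive children, so it may not carry over. For anti-PEG antibodies no figure can be given.

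Nor do the documents show that 16 weeks is the wrong threshold. SAP 8.3 says that its approach follows regulatory guidance and a white paper, which are outside this review. What can be said is that this schedule cannot apply the threshold.

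**What to change.** Keep the 16-week threshold and make its limits visible.

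1. In SAP 8.3 and in the footnotes of the persistent and transient tables, state that 16-week persistence cannot be met on the scheduled visit days, so a zero is not evidence that persistent antibodies are absent.
2. For each antibody type (anti-hGH binding, anti-hGH neutralizing, anti-PEG), add two rows:
   - treatment-induced and positive at both Visit 2 and Visit 3/ET, with the interval in days from actual sample dates;
   - positive at the last available sample only (duration indeterminate).
3. Do not describe subjects in either row as transient. This needs one sentence in the transient definition. On scheduled samples, the count under the present definition is recovered by adding the two rows back, so comparison with analyses that use the rule unchanged is not lost.
4. Any subject whose positives span 112 days or more stays persistent under the existing rule.
5. For children positive at baseline, say what counts as positive in the new rows, for example only samples that meet the 4-fold titer rule.

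The cost is SAP wording and table shells. No new samples, visits or assays are needed.

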8.4. IGF-1 SDS

A descriptive table including the number and percentages of subjects by visit will be presented where:

- IGF-1 SDS > 2.0
- IGF-1 SDS > 3.0

Listings of IGF-1 and IGF-1 SDS for subjects with abnormally high IGF-1 SDS will be generated.

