8.1 Trial Entry Criteria

8.1.1 Inclusion Criteria

- 1) Investigator-determined GHD diagnosis together with at least one of the following prior to the historical initiation of daily hGH therapy:
 - a. 2 GH stimulation test(s) with peak GH level of ≤ 10 ng/mL
 - b. Impaired height defined as at least one of the following:
 - i) ≥ 2 SD below the mean height for chronological age and sex when compared to the relevant growth charts:
 - (1) 2006 WHO Child Growth Standards for < 2 years old

- (2) 2000 CDC Growth Charts for the United States for ≥ 2 years old
 - ii) ≥ 1.5 SDS below mid-parental height
 - c. IGF-1 level ≥ 1 SD below the mean IGF-1 level standardized for age and sex according to the local laboratory reference values
 - d. Bone age x-ray ≥ 6 months less than chronological age
 - e. Diagnosis of at least one additional pituitary hormone deficiency
 - f. Congenital hypopituitarism due to congenital hypothalamic-pituitary defect (eg, ectopic posterior pituitary, pituitary hypoplasia, abnormal stalk, septo-optic dysplasia) or genetic defect (eg, GH1, POU1F1, or PROP1)
- 2) 6 months to 17 years old, inclusive, at Visit 1
 - a. If 3 to 17 years old, are taking daily hGH at a dose of ≥ 0.20 mg hGH/kg/week for at least 13 weeks but no more than 130 weeks prior to Visit 1
 - b. If ≥ 6 months but < 3 years old, are either hGH treatment-naïve or are taking daily hGH at a dose of ≥ 0.20 mg hGH/kg/week for no more than 130 weeks prior to Visit 1
- 3) Tanner stage < 5 at Visit 1
- 4) Open epiphyses (bone age ≤ 14.0 years for females or ≤ 16.0 years for males)
- 5) Written, signed, informed consent of the parent or legal guardian of the subject and written assent of the subject as required by the IRB/HREC/IEC

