9.5 Selection of Trial Doses

TransCon hGH is an inactive prodrug. The phase 2 pediatric GHD trial with TransCon hGH demonstrated that a dose of 0.21 mg hGH/kg/week provided similar hGH exposure, efficacy (annualized HV), and safety/tolerability compared to the equivalent weekly dose of Genotropin, with PD demonstrating normalization of IGF-1 SDS. This trial also demonstrated comparable tolerability and safety and numerically greater annual HV with a 0.30 mg/kg/week dose of TransCon hGH. Treatment guidelines support initiation of hGH at a dose of 0.24 mg hGH/kg/week ([Grimberg 2016](#)). The TransCon hGH 0.24 mg hGH/kg/week dose is currently being studied in the phase 3 heiGHt Trial. To align the starting dose across the TransCon hGH program, the same dose has been chosen for the current trial. Given non-compliance rates on daily hGH doses versus the expected increased compliance in this trial, even subjects entering on 0.30 mg hGH/kg/week will likely do well on the lower TransCon hGH dose. Importantly, IGF-1 levels, along with other safety parameters discussed in [Section 9.6](#), will be measured at Visit 2 (and the C_{max} Visit, as applicable) and, if needed, changes in dosing allowed.

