9.9.1.1 Previous hGH Therapies

At Visit 1, subjects ≥ 3 years old must be on current daily hGH (≥ 0.20 mg hGH/kg/week) for ≥ 13 weeks and ≤ 130 weeks, while subjects ≥ 6 months to < 3 years old may be either treatment-naïve or be on current daily hGH (≥ 0.20 mg hGH/kg/week) for ≤ 130 weeks. The current hGH name, dose, injection device type, and start date will be recorded on the appropriate eCRF page. Subjects should remain on a stable dose between Screening and Visit 1.

Subjects are to be instructed to take their regular dose of hGH the evening before Visit 1 but NOT on the day of Visit 1.

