3.3. STUDY ENDPOINTS

3.3.1. Safety Endpoints

The safety endpoints as measured throughout the 26 weeks of weekly TransCon hGH treatment include the following:

- Incidence of AEs
- Local tolerability, as assessed by the subject/parents/legal guardians/caregivers and trial staff
- Incidence of antibodies against hGH, including neutralizing antibodies
- Incidence of antibodies against PEG
- Incidence of IGF-1 SDS >2.0, >3.0 with confirmation
- Parameters of HbA1c and lipids
- Hormone levels, including thyroid status and morning cortisol
- All other hematology and chemistry parameters
- Vital sign measurements

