5.1. BASELINE DATA

Baseline will be defined as the most recent non-missing assessment (including repeated and unscheduled assessments) before the study drug administration.

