9.3. IGF-1 SDS AND IGFBP-3 SDS

A descriptive table including the frequency and percentages of subjects by each visit will be presented where:

- $0 \leq \text{IGF-1 SDS} \leq 2.0$
- $-2.0 \leq \text{IGF-1 SDS} \leq 2.0$
- $-1.0 \leq \text{IGF-1 SDS} \leq 2.0$
- $\text{IGF-1 SDS} > 2.0$
- $\text{IGF-1 SDS} > 3.0$

The by visit post baseline values and change from baseline in IGF-1 SDS and IGFBP-D SDS will be analyzed by ANCOVA model, including baseline age, peak GH (log transformed) at diagnosis, baseline (of the corresponding variable), prior GH dose level (log transformed), and duration (log transformed) as covariates, and gender as a factor.

The absolute values and change from baseline at each visit of the IGF-1, IGFBP-3, IGF-1 SDS and IGFBP-3 SDS will be also presented with descriptive statistics. Listings will be generated for these outcomes.

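### The planned tables of IGF-1 SDS above 2.0 and above 3.0 give prevalence at each visit, although the endpoint is confirmed incidence, and do not show how many children became newly elevated on TransCon hGH

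*SAP*

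**What the plan says.** **Endpoint.** SAP 3.3.1 lists "Incidence of IGF-1 SDS >2.0, >3.0 with confirmation" among the safety endpoints measured throughout the 26 weeks. Protocol 14.1.1 has the same endpoint, written with ≥ in place of >.

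**Analysis.** SAP 8.4 states: "A descriptive table including the number and percentages of subjects by visit will be presented where" IGF-1 SDS is above 2.0 and above 3.0. Its only other output is at subject level: "Listings of IGF-1 and IGF-1 SDS for subjects with abnormally high IGF-1 SDS will be generated". SAP 9.3 repeats both cut-offs under efficacy: "A descriptive table including the frequency and percentages of subjects by each visit will be presented where". It adds descriptive change from baseline in IGF-1 SDS and an ANCOVA adjusted for the baseline value.

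**Baseline.** SAP 5.1: "Baseline will be defined as the most recent non-missing assessment (including repeated and unscheduled assessments) before the study drug administration". The schedule of events has no blood draw at Visit 1, so for IGF-1 this is a Screening sample. Protocol 8.1.1 requires of the older children: "If 3 to 17 years old, are taking daily hGH at a dose of ≥ 0.20 mg hGH/kg/week for at least 13 weeks". Protocol 9.9.1.1 adds: "Subjects should remain on a stable dose between Screening and Visit 1". Protocol 9.5 foresees entry on a daily dose above the trial dose of 0.24 mg hGH/kg/week: "even subjects entering on 0.30 mg hGH/kg/week will likely do well on the lower TransCon hGH dose". The only IGF-1 entry criterion concerns a low value before daily hGH was first started. Nothing in Protocol 8.1 sets an upper limit at Screening or Visit 1.

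**Related sections.** SAP 8.5 plans shift tables from baseline for laboratory parameters where applicable, but its parameter list omits IGF-1. SAP 8.3 does link antibodies to baseline: it reports pre-existing positivity separately and defines treatment-emergent positivity against the pre-treatment sample.

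**The concern.** Incidence over a treatment period counts children who reach the state during that period. A percentage above a cut-off at a visit counts everyone in that state at the visit, including those in it before the first dose. In this trial the two can differ, because most children enter on daily hGH and a high IGF-1 does not bar entry.

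Protocol 5.4 gives the primary aim as the safety of switching from daily to weekly hGH. For IGF-1, a reader will want to know how many children who were not above +2.0 (or +3.0) on daily hGH were above it on TransCon hGH. The planned tables do not give that number.

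Two further features move the by-visit count away from the endpoint:

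- Protocol 9.6.2 allows a dose reduction after a confirmed value above +2.0. A child newly high at Visit 2 may therefore be absent from the Visit 3 count, and no count of children ever newly elevated is planned.
- SAP 5.3 maps unscheduled samples to scheduled windows and keeps the one nearest the target day. A confirmatory retest can therefore replace the value that prompted it.

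**Working it through.** **The plan's own figure.** SAP 3.2 gives at least 95% probability of observing an event with 2% incidence in 150 subjects, and with 1% incidence in about 300. The formula is 1 − (1 − p)^n:

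- 1 − 0.98^150 = 0.9517
- 1 − 0.99^300 = 0.9510

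Both reproduce. The point below does not depend on them.

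**What the by-visit tables leave open.** Let N be the number of children, B the number above 2.0 at baseline and P the number above 2.0 at a visit. If only B and P are known, the number newly elevated lies between

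max(0, P − B) and min(P, N − B),

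and the at-risk denominator is N − B. N = 150 is the planned size. The documents give no IGF-1 rates, so the rates below are assumed, with no missing data.

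| Baseline | Visit | B | P | Newly elevated | At risk (N − B) | % of at risk |
|---|---|---|---|---|---|---|
| 10% | 10% | 15 | 15 | 0 to 15 | 135 | 0% to 11.1% |
| 5% | 10% | 8 | 15 | 7 to 15 | 142 | 4.9% to 10.6% |
| 20% | 20% | 30 | 30 | 0 to 30 | 120 | 0% to 25.0% |

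(5% of 150 is 7.5, taken as 8.)

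First row: the lower limit is max(0, 15 − 15) = 0, where the same 15 children are high both times. The upper limit is min(15, 135) = 15, where all 15 baseline cases fell and 15 others rose. Then 15/135 = 11.1%.

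**Across visits.** With 15 children high at Visit 2 and 15 at Visit 3, the number ever high after baseline lies between 15 (the same children) and 15 + 15 = 30 (no overlap), or 10% to 20% of 150. Two by-visit columns cannot say which.

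**Retest in the same window.** SAP Table 2 sets the Visit 2 target at Day 92 and its window at Days 61 to 137. Take a Visit 2 sample on Day 83, within the allowed days, and a retest on Day 97, also 5 days after a weekly dose. The distances from target are 92 − 83 = 9 and 97 − 92 = 5. The retest is nearer and is the value tabulated. If it is at or below 2.0, the first elevation leaves the table.

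**The case against.** **The listings allow a count.** SAP 8.4 and 9.3 both promise IGF-1 listings, and SAP 5.3 says listings include all data points. A reader might infer from the tables that newly elevated children cannot be counted at all. That goes too far: with about 150 children a hand count is possible if baseline values are shown, which 8.4 does not state. What stands is that a named safety endpoint would have no tabulated result.

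**IGF-1 is linked to baseline elsewhere.** This is true on the continuous scale: SAP 9.3 plans within-child change and a baseline-adjusted ANCOVA. Neither shows who crossed a cut-off. If by-visit reporting includes Screening, which the SAP does not say, the net change would be visible but individual transitions would not.

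**The shift tables in SAP 8.5 may cover IGF-1.** The protocol lists IGF-1 under laboratory assessments, so coverage is ambiguous. The 8.5 list omits it, however, and gives no category above 3.0.

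**The analysis is descriptive.** This is correct. A reader might infer a loss of power from ignoring the pairing, but no test of these proportions is planned, so there is none to lose.

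**The proportion above +2.0 on drug is a legitimate exposure summary.** This too is correct, and Protocol 9.6 acts on the level itself. It is a reason to keep the by-visit percentages, not to call them incidence.

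**Conclusion.** The point holds for the planned threshold tables. They report visit prevalence under an endpoint defined as confirmed incidence over 26 weeks, and they do not separate children already high at baseline from those newly high on TransCon hGH. At an assumed 10% before and 10% after, the same tables fit 0 to 15 newly elevated children (0% to 11.1% of 135). The width of that range depends on the assumed rates. That a range exists does not, provided some children are high at baseline and some at the visit.

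A reader might also infer that a baseline-linked count would show the switch pushing children above the cut-off. The documents do not support that. There is no control arm, and regression to the mean, puberty and the different sampling time relative to dosing (daily injections at Screening, about 5 days after a weekly dose at Visits 2 and 3) remain as explanations. The count describes what happened to the children; it does not attribute it.

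This is a gap in tabulation that should be closed. It is not a flaw in the design or the data collection.

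**What to change.** In SAP 8.4:

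1. Define treatment-emergent IGF-1 SDS >2.0 (and >3.0) as a post-dose value above the cut-off in a child at or below it at baseline.
2. Report it at each visit and at any post-baseline visit, with children at or below the cut-off at baseline as the denominator.
3. Give each count twice: for any value, and for values confirmed by the repeat sample. Protocol 9.6.2 describes the repeat only for values found at Visit 2 or the C_max Visit, so state how an elevation first seen at Visit 3 is classed.
4. Where a retest falls in the same analysis window, keep the original value for these counts.
5. Add baseline-by-Visit 2 and baseline-by-Visit 3 shift tables with categories <0, 0 to 2.0, >2.0 to 3.0 and >3.0, showing hGH-naive children separately because their baseline is untreated.
6. Keep the by-visit percentages in 8.4 and 9.3, labelled as an exposure summary, and state whether they include baseline.

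A descriptive paired difference in proportions with a confidence interval is optional.

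The cost is SAP wording and an extra table from data already collected. The at-risk denominator is slightly smaller than the Full Analysis Set.
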